## **2. HYPOTHESIS AND OBJECTIVES**

### **2.1. Hypothesis**

The hypothesis is that ridge dimensional reductions in the sites of immediate implant combined with autogenous tissue graft/acelluar dermal matrix are significantly less than the sites of immediate implant alone. Soft tissue augmentation is able to increase gingival thickness and limit resorption of bone by expanding the dimension of peri-implant mucosa. In addition to limited changes of ridge dimension and increased gingival thickness, stable gingival level and increased width of keratinized gingiva could also be found following soft tissue augmentation.

Placement of acellular dermal matrix has comparable clinical outcomes to placement of autogenous tissue graft because the clinical trials of mucogingival surgery, such as root coverage, show acellular dermal matrix is as effective as autogenous tissue graft.

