### **2.3. Secondary Objectives**

In addition to the esthetics-related clinical outcomes, the change of bony structure will also be measured. The alteration of bony structure around an implant is an important clinical parameter indicating the long term stability of the implant. The radiographic change of alveolar bone level will be measured on the images of periapical radiograph. The change of bone dimension will be measured on the images of cone beam computed tomography (CT)

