#### **3.3. Inclusion Criteria**

Forty two subjects will be recruited among the patients attending the Clinic for Graduate Periodontics, UTSD, and the Clinic of PISH, who are in need of a tooth extraction at the maxillary premolar, canine and incisor region, and subsequent single implant placement. The reasons for extraction will include poor endodontic prognosis and/or unrestorable teeth (extensive caries, traumatic fractures, fractures of endodontically treated teeth, root perforation, root resorption with or without radiographic periapical lesion up to 3 mm in diameter). All subjects are  $\geq 18$  year-old and systemically healthy or with controlled common systemic conditions (controlled hypertension, controlled diabetes HbA1c up to 7 %). The adjacent teeth have to be present and the eligible tooth has esthetically acceptable buccal gingival margin position prior to surgery, compared to neighboring teeth and contralateral tooth, and adequate width of buccal keratinized gingiva( $\geq 3$ mm). The level of radiographic bone

level has the distance from CEJ to interproximal crest up to 4 mm.

Location of buccal alveolar crest has to be generally within 4 mm from the free gingival margin, verified after the extraction, before randomization; and fenestration, if present, up to 3mm in diameter at the apical part of the root and affecting less than 30% of the buccal socket wall.

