### 6.3. Study Visits and Procedures

#### a. Screening Visits and Procedures

Study protocol and consent forms will be approved by the Institutional Review Board at the University of Texas Health Science Center at Houston. The trial will be registered with ClinicalTrials.gov. The clinicians and dental students in UTSD and PISH will be told the information of this clinical trial. The potential subjects who are interested in participating in this project will be referred to the clinic of Department of Periodontics and Dental Hygiene, UTSD or the clinic of PISH for initial screening. The principal investigator will confirm the eligibility of these patients. All patients will have dental cone-beam computed tomography before the surgery given the implants will

be placed in the highly esthetic zone (Benavides et al. 2012). All patients will sign the consent forms and are informed of the details of study procedures as well as potential complications. After informed consent is obtained, and initial periodontal therapy and oral hygiene instruction, whenever indicated, the surgery will be scheduled as the first visit.

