At the first appointment, all clinical measurements will be performed (probing depth (PD), clinical attachment level (CAL), bleeding on probing (BOP), plaque index (PI)) and the impression of maxillary and mandibular dentition will be taken. One periapical radiography of the surgical site will be taken after the surgery is finished. After verification that the local anatomical inclusion criteria are met, patients will be randomized to one of three treatment groups. All implants will be placed according to standard protocol at a subcrestal position (1 mm below the buccal crest) engaging the palatal wall without elevation of a mucoperiosteal flap. The gap between the implant and alveolar bone will be filled with xenograft (Geistlich Bio-Oss®) and covered by collagen dressing (CollaTape®). In the groups having soft tissue augmentation, intrasulcular incisions will be carried out to partially dissect the buccal flap from mesial papilla to distal papilla. The SCTG or ADM will be inserted into the dissected buccal flap. The SCTG will be subepithelially harvested from the palate of the patient. The width of tissue graft will be equal to the distance between the interproximal papillae on the level of buccal gingival margin. The length of SCTG will be standardized as 10 mm. The thickness of SCTG will be standardized as 1-1.5mm. The size of ADM will be standardized following the same principle. The SCTG tissue graft or ADM will be stabilized by sling suture (chromic gut 5-0).

In the three groups, the straight healing abutment will be delivered immediately after implant placement provided that the implant shows primary stability and has engaged in the bone with an insertion torque of 25 Ncm or more (Norton 2004). In case of a lower insertion torque, the protocol will be abandoned, a cover screw will be placed, and a two stage implant protocol will be followed. All patients will receive a permanent restoration at 6 months after surgery, if the implant is deemed to be successful (Misch et al. 2008). The placement of xenografts aims to optimize the esthetic outcomes.

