#### *b. Study Visits and Procedures*

A stent with reference notches made by #1/2 bur at a 2 mm distance from the gingival margin at the mesio-buccal, mid-buccal and disto-buccal sites will be fabricated. The stent will be made based on the patient's dental model to have the best fit. A new stent with the same design will be made after patients have permanent restorations and the stent will be used to measure the parameter at the 12-month follow-up

The following measurements will be carried out at the visits:

- 1) Soft tissue distance from each of the three notches (mesio-buccally, mid-buccally and disto-buccally, respectively): the distance is measured from the notch to the gingival margin at three sites; it is measured at implant placement visit (baseline), 3 months, 6 months, and 12 months.
- 2) Horizontal defect dimension (HDD) defined as horizontal distance from the implant shoulder to the buccal alveolar socket wall, measured in the mid-buccal site; it is measured only at implant placement visit (the first visit).
- 3) Vertical defect dimension (VDD) defined as vertical distance from implant shoulder to the apical contact with the socket wall, measured in the mid-buccal site; it is measured only at implant placement visit (the first visit).
- 4) Buccal soft tissue thickness will be measured following the extraction using the endodontic file and the digital caliper (one measurement/ mid-buccal/6mm apical to gingival margin); it is measured before and after implant surgery at the first visit, 6 months and 12 months.
- 5) Probing depth (PD): probing depth is defined as the distance from the gingival margin to the tip point of the probe (Williams probe). PDs will be measured at 6 sites per tooth (mesio-buccal, mid-buccal, disto-buccal, disto-palatal, mid-palatal, mesio-palatal); it is measured before surgery at the first visit, 3 months, 6 months and 12 months.
- 6) Bleeding on probing (BOP): the prevalence of bleeding on probing at six sites (mesio-buccal, mid-buccal, disto-buccal, disto-palatal, mid-palatal, mesio-palatal) of the tooth/implant will be documented at the first visit, 3 months, 6 months and 12 months.
- 7) Plaque index (PI): A periodontal probe will be swept along each site to all the teeth to identify the presence or absence of plaque accumulation at the first visit, 3 months, 6 months and 12 months. A dichotomous scoring system will be used with one (1) and zero (0) equaling presence and absence, respectively, of plaque.

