- 8) Buccal-palatal dimension of the ridge at the site of implant placement: the dimension will be measured at different reference points (3 mm, 6 mm from the baseline gingival margin) on the study model. Impressions for study models will be taken at the first visit, at 3 months, 6 months and 12 months. The measurement will be done by the digital caliper and the computer assisted scanned images.
- 9) Buccal plate thickness: it will be measured on the images of dental cone beam computed tomography. The patients will have the images taken with a stent before the surgery and 6 months after the surgery. The stent will be made based on the patient's dental model. The midline of the implant site will be buccally and palatally marked with gutta percha.
- 10) Interproximal bone level: a film holder with silicon putty to aid in reproducibility of the radiograph position will be used. The mesial and distal crestal bone level will be measured using the MIPACS software. Implant platform will serve as the reference point. Vertical and horizontal changes (depth and width of the vertical defect on the mesial and/or distal aspect of the implant, if present) will also be measured from radiographs taken at the time of completion of surgery, at 6 and 12 months. Dose and frequency of x-rays in the study are standard of care for any implant patient in UTSD, PISH or in standard clinical practice, and are not altered for the purpose of the study. (Medical status is updated and recorded at each visit, including verification that female patients are not pregnant prior to x-ray taking; this is also standard of care).
- 11) The diameter of the apical radiolucency, when initially present, will be monitored radiographically. Any lesions present in the radiography will be assessed immediately after surgery and 6 months.
- 12) Blood flow of gingiva: The laser Doppler flowmeter is a noninvasive measure of capillary blood perfusion. The readings are obtained by placing the tip on the

surface of buccal gingival. It is measured before and after implant surgery at the first visit, 3 months, 6 months and 12 months.

*c. Final Study Visit:*

The 12-month follow-up will be the subject's last visit for this clinical trial. The patients will have clinical measurements (PD, BOP, PI), dental impressions taken, and periapical radiographic examination. All subjects will have periodontal maintenance in the periodontics clinic of UTSD or PISH in the future.

*d. Post Study Follow up and Procedures*

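### Bone-dimension change rests on a CBCT buccal plate thickness that is not the same quantity before surgery and at 6 months, so bone loss can read as gain

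*Combined protocol and SAP*

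**What the plan says.** Sections 3.1 and 5.1 list bone dimension among the secondary outcomes, and section 2.3 says that its change will be measured on cone beam CT. Section 6.3 b, measurement 9, supplies the only CT reading: "Buccal plate thickness: it will be measured on the images of dental cone beam computed tomography". On timing it says: "The patients will have the images taken with a stent before the surgery and 6 months after the surgery". A stent with gutta percha marks the midline of the site on the buccal and palatal sides. The measurement names no inner or outer border and no level, and it does not say whether graft in the gap counts as plate.

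The site changes between the two scans. Section 6.3 a states: "All patients will have dental cone-beam computed tomography before the surgery". Extraction comes later: section 3.3 has the buccal crest position "verified after the extraction, before randomization", and section 6.1 places allocation after extraction. Under section 6.3 a the implant then engages the palatal wall in every arm, and "The gap between the implant and alveolar bone will be filled with xenograft". The only image planned straight after surgery is a periapical film.

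The gap is recorded once, at placement, as measurement 2: "Horizontal defect dimension (HDD) defined as horizontal distance from the implant shoulder to the buccal alveolar socket wall". No use of it in the CT outcome is stated. Section 11.2 c tests secondary outcomes between arms by one-way ANOVA and over time within each arm by paired t-test.

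**The concern.** At the first scan, buccal plate thickness has a natural meaning: the bone between the root surface and the outer cortex. At 6 months there is no root. The bone lying outside the implant may then consist of the old plate plus the filled gap, less whatever has resorbed. Subtracting the first reading from the second would compare two different structures under one name.

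Section 2.1 makes a claim about bone itself: "Soft tissue augmentation is able to increase gingival thickness and limit resorption of bone by expanding the dimension of peri-implant mucosa". The other planned measures do not isolate buccal bone. The primary outcome is ridge width on study models, which includes soft tissue and therefore the 1 to 1.5 mm graft placed under the buccal flap in two of the arms. The periapical films read mesial and distal levels only. The CT is the one direct view of buccal bone, so a change score that can have the wrong sign would undermine any conclusion about resorption.

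**Working it through.** The plan gives no sample size, expected value or standard deviation for the CT outcome, so there is no figure of its own to reproduce. The check is algebraic, with an illustration.

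**Inputs**
- B: plate thickness at the first scan, with the tooth in place (inferred from visit order). It cancels below.
- G: buccal gap at the level measured. The documents give no value; 0.5 to 3 mm is assumed.
- L: loss at the outer buccal surface. Section 1.1 gives about 1 to 1.5 mm within one year for sites without bone or tissue graft.

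**Step 1. Two possible 6-month readings**

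Implant surface to outer bone surface, with the filled gap counted:
- 6-month reading = B + G - L
- Change = (B + G - L) - B = G - L

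Native plate only, with the graft excluded and loss taken at the outer surface:
- 6-month reading = B - L
- Change = (B - L) - B = -L

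The two rules differ by G. Measurement 9 does not choose between them.

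**Step 2. Size under the first reading (change = G - L, mm)**

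| Assumed gap G | L = 1.0 | L = 1.5 |
|---|---|---|
| 0.5 | -0.5 | -1.0 |
| 1.0 | 0.0 | -0.5 |
| 1.5 | +0.5 | 0.0 |
| 2.0 | +1.0 | +0.5 |
| 2.5 | +1.5 | +1.0 |
| 3.0 | +2.0 | +1.5 |

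The apparent change runs from -1.0 to +2.0 mm while the outer surface has in fact lost 1.0 or 1.5 mm. The sign turns to gain as soon as G exceeds L. If loss is smaller in these xenograft-filled sites, the turn comes sooner: with an assumed L of 0.5 mm, any gap above 0.5 mm reads as gain.

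**Step 3. Which tests are affected**
- Within an arm, the paired t-test targets the mean of G - L. It can show a significant gain where the outer surface has resorbed.
- Between arms a and b, the expected difference in change is (mean G in a - mean G in b) - (mean L in a - mean L in b). Implant position and gap fill are specified alike for all arms. If mean gaps are equal, the first bracket is zero and the contrast is the difference in loss, without bias.
- Spread: Var(G - L) = Var(G) + Var(L) - 2 Cov(G, L). This exceeds Var(L) when Var(G) is larger than 2 Cov(G, L). The documents give none of these terms.

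**Step 4. What the alternatives measure**
- Total bone width, outer cortex to outer cortex: change = -(buccal loss + palatal loss). G does not enter.
- Displacement of the outer buccal surface: change = -L. G does not enter.

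**The case against.** The strongest reply is that the implant-surface border is an inference. Measurement 9 does not state it, a reader of the scans might be able to tell native plate from graft, and the case report form listed as an attachment, which is not among the pages available, may define landmarks. Nor does measurement 9 say that it is the bone-dimension outcome, and the palatal stent mark would also suit a full-width reading. All of this stands, and it makes the result conditional. It does not remove the problem: no other CT reading is defined, and nothing in the text rules out the reading that gives G - L.

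The gap is also not constant with depth. Measurement 3 (vertical defect dimension) runs down to the point where implant and socket wall meet, and there the gap is zero. At a deep enough level the distortion vanishes. Since no level is fixed, this is further reason to state one.

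Three stronger readings are tempting and are not supported:
- **A reader might infer that the plan will report a bone gain.** The table has negative cells: with gaps of 0.5 to 1 mm the result is -1.0 to 0 mm. No gap value is given, and the 1 to 1.5 mm loss is for ungrafted sites within one year, whereas every arm here receives xenograft and the scan is at 6 months.
- **A reader might infer a definite loss of precision.** That needs a gap SD, which the documents do not give. The 0.85 mm (section 3.1) and 0.9 mm (section 11.1) SDs are for ridge change, not for a CT plate reading.
- **A reader might infer a biased comparison between arms.** The implant is placed after allocation by an unblinded surgeon, so equal gaps are not guaranteed. But the prescribed position and fill are common to all arms, and nothing in the documents indicates that gaps differ by arm.

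Two existing measurements help only in part. Buccal soft tissue thickness, 6 mm from the margin, could help separate soft tissue from ridge width on the models, but the plan does not combine them. The recorded gap could be used to adjust the CT change, but it is taken at the implant shoulder only and arises after randomization.

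**Conclusion.** The concern holds in conditional form. As written, the pre-surgery and 6-month plate readings are comparable only if readers can separate the original plate from the grafted gap, and no rule asks them to. Under the implant-surface reading the change is gap minus loss. Its illustrative range of -1.0 to +2.0 mm rests on assumed gaps, on the section 1.1 loss for ungrafted sites, and on the graft being read as bone. The damage is to the within-arm paired test and to any absolute statement about resorption. The ANOVA between arms is not biased in expectation by the shared fill, though it may carry extra variance from the gap. The outcome is secondary and the primary ridge measure is untouched, so this should be corrected but does not threaten the main analysis.

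**What to change.** In section 6.3 b, define bone-dimension change by a quantity present on both existing scans. Use either total buccal-palatal bone width from outer cortex to outer cortex, or displacement of the outer buccal bone surface. State the levels, and take the readings on the stent-marked midline or after aligning the scans on the adjacent teeth, which section 3.3 requires to be present. Total width combines buccal and palatal loss; surface displacement isolates the buccal side but depends more on alignment.

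Keep the 6-month implant-to-outer-cortex thickness as a follow-up value compared between arms, and do not analyse it as change from the pre-extraction plate. In section 11.2 c, name the new measure as the one to which the ANOVA and paired t-test apply, and base any statement on bone resorption on it.

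The cost is rewording in two sections, some extra image-reading work and a small alignment error. No additional scan or visit is needed.

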## **7. TRIAL MATERIALS**

### **7.1. Trial Product (s)**

Implants, bone grafts (Bio-Oss) and collagen dressing (CollaTape®) will be used following the indications approved by Food and Drug Administration (FDA). Implants will be placed to support the crowns to restore patients' oral esthetics and functions. Bone grafts are placed to preserve the socket dimension following extraction. Collagen dressing is placed to cover the bone grafts and extraction wound.

AlloDerm® Regenerative Tissue Matrix (RTM) is the one of the most widely used substitutes for autogenous tissue graft in dentistry. It is an acellular dermal matrix (ADM) that is derived from donated human skin and is minimally processed to remove epidermal and dermal cells with nondenaturing detergent while preserving the extracellular matrix. The removal of viable cells and antigens during the decellularization process minimizes the risk of rejection and inflammation at the surgical site. Then, a cyropreservant is added to avoid crystal formation, and the resulting tissue matrix is freeze-dried (Wang et al. 2015). The remaining matrix serves as a framework for cellular infiltration and vascularization. ADM is indicated for soft tissue augmentation (Batista et al. 2001; Griffin et al. 2004; Park and Wang 2006), gingival recession defect coverage (Andrade et al. 2008; Tal et al. 2002), keratinized gingiva extension (Harris 2001; Yan et al. 2006), and extraction socket coverage (Fowler et al. 2000; Froum et al. 2004; Park 2011) for both teeth and implants. Basically, ADM can be used in all the procedures that the autogenous tissue graft is indicated for.

## **7.2. Storage and Drug Accountability**

Implants, bone grafts, collage dressing, and AlloDerm® Regenerative Tissue Matrix will be stored at room temperature in its original packaging following the manual instruction. The expiration date for the product is recorded on the product container labeling as year (4 digits) and month (2 digits) and the product expires on the last day of the month indicated. Expiration date printed on the labeling is valid as long as product is stored at room temperature and in an unopened foil pouch/packaging. Once the product is expired, the material will be discarded.

# **8. TREATMENT**

## **8.1. Rationale for Selection of Treatments**

Although subjects will be assigned to different experimental groups, all treatments are conducted following general clinical principles. The details of procedure are mentioned in section 6.3.

## **8.2. Specific Restrictions / Requirements**

Subjects will be instructed to discontinue brushing the surgical area, to use mouth rinse (Chlorhexidine 0.12%) twice daily during the first two weeks and to avoid biting at the surgical area for at least two months.

## **8.3. Blinding**

The surgeons and patients cannot be blinded because the surgeons will be told which procedure to perform at the first visit and patients will be aware of the procedures that they received after surgery. The patients will be informed of benefits of all the procedures and realize all procedures are supported by scientific evidence.

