### **3. STUDY POPULATION**

#### **3.1. List the number of subjects to be enrolled.**

**The primary outcome is ridge dimensional alteration at six months after surgery while the secondary outcomes are changes of gingival level, gingival thickness, width of keratinized gingiva, alveolar bone level and bone dimension.** Based on the preliminary results, 11 subjects per group need to be recruited to have 80% power to detect a 1 mm difference with 0.85 mm standard deviation in ridge dimensional change between groups. We plan to enroll 14 subjects in each group to account for potential dropout. The subjects will be recruited from the patients enrolled in the clinics of University of Texas Health Science Center at Houston School of Dentistry (UTSD) and Periodontal and Implant Surgeons of Houston (PISH). There will be no restriction on gender or race.

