## 6. METHODS AND ASSESSMENTS

### 6.1. Randomization and Blinding

Patient allocation to the three groups (immediate implant combined with SCTG, immediate implant combined with ADM, immediate implant alone) was performed by a blinded non-surgeon following tooth extraction, based on computer-generated randomization (MATLAB). The surgeon will be noticed the randomization results the date of performing surgery. Patients will not be blinded given the patients definitely know the treatments that they receive due to the characteristics of procedures.

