## **10. DATA ANALYSIS**

### **10.1. Data Quality Assurance**

Data and measurements will be checked by two separate sub-investigators ([name], [name]) as well as analyzed statistically to ensure that the data obtained is accurate, complete and reliable.

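### No section requires cast, CBCT or radiograph readings to be made without knowledge of arm, so the ridge-dimension primary outcome is open to avoidable reader bias

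*Combined protocol and SAP*

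**What the plan says.** Two sections set the blinding policy.

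- Section 6.1: allocation is done by a blinded person who is not a surgeon. For patients: "Patients will not be blinded given the patients definitely know the treatments that they receive due to the characteristics of procedures".
- Section 8.3: "The surgeons and patients cannot be blinded". The section says nothing about outcome assessors.

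The outcome and its measurement are described elsewhere.

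- Section 3.1: "The primary outcome is ridge dimensional alteration at six months after surgery". (Section 5.1 gives six and 12 months. The point applies to either.)
- Section 6.3 b, item 8: "the dimension will be measured at different reference points (3 mm, 6 mm from the baseline gingival margin) on the study model". Then: "The measurement will be done by the digital caliper and the computer assisted scanned images".
- Section 6.3 b, items 9 and 10: buccal plate thickness is read from CBCT images, and interproximal bone level from periapical radiographs with measurement software.
- Section 10.1: "Data and measurements will be checked by two separate sub-investigators". Nothing is said about masking, or about whether these two people also operate.
- Sections 12.3 and 14: each subject gets a coded number. The stated purposes are confidentiality and record keeping.

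**The concern.** The reason in Section 8.3 for not blinding is that the surgeon must know the procedure and the patient will notice it. That reason does not reach a cast or an image, which can be read later and away from the patient. The plan leaves this step unprotected: it does not say who reads, whether the reader is separate from the surgeon, or whether arm is concealed.

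Reading the primary outcome needs judgement. Points 3 mm and 6 mm from the baseline gingival margin have to be located on later casts, and a caliper or a scan measurement placed there. The hypothesis in Sections 2.1 and 11.1 is directional, with less reduction in the graft arms, so a reader who knows the arm also knows which direction is hoped for. Any resulting shift goes straight into the between-group difference, and no analysis in Section 11.2 could detect or correct it.

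**Working it through.** **1. Coverage of the plan**

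| Step | Section | Masking to arm stated? |
|---|---|---|
| Allocation | 6.1 | Allocator described as blinded |
| Patient | 6.1, 8.3 | Not blinded |
| Surgeon | 8.3 | Not blinded |
| Ridge dimension on casts and scans | 6.3 b, item 8 | Reader and masking not stated |
| Buccal plate on CBCT | 6.3 b, item 9 | Reader and masking not stated |
| Bone level on radiographs | 6.3 b, item 10 | Reader and masking not stated |
| Checking of measurements | 10.1 | Two checkers, masking not stated |
| Subject codes | 12.3, 14 | Not described as hiding arm |

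**2. The plan's own figure**

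Inputs: 11 per group, 80% power, 1 mm difference, SD 0.9 mm (Section 11.1) or 0.85 mm (Section 3.1). The significance level is 0.05, with sidedness not stated (Section 11.2). For a two-sample t-test with n per group, SE = SD × √(2/n), on 2n − 2 degrees of freedom.

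- SD 0.9, n = 11: SE = 0.9 × √(2/11) = 0.384, noncentrality 1/0.384 = 2.61. One-sided 0.05 gives 80.8% power, so the stated 11 is reproduced.
- Two-sided 0.05 with 11 per group gives 69.8% (SD 0.9) or 74.7% (SD 0.85).

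This has no bearing on masking. It shows only which n and SD the illustration should use: 11 (stated requirement) to 14 (planned enrolment, Sections 3.1 and 11.1), and SD 0.85 to 0.9.

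**3. Illustration of reader bias**

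Assumption, not taken from the documents: with no true difference, readings favour a graft arm by b = 0.1, 0.2 or 0.3 mm on average, and the SD is unchanged. The estimate then shifts by b, which is 10%, 20% or 30% of the 1 mm target.

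The chance of a significant two-sided result is P(|T| > c), where T is noncentral t with 2n − 2 degrees of freedom and noncentrality b/SE, and c is the critical value. Example with n = 14, SD 0.85, b = 0.3: SE = 0.85 × √(2/14) = 0.321, noncentrality 0.3/0.321 = 0.93, c = 2.056, result 14.7%.

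| n per group | SD (mm) | b = 0.1 | b = 0.2 | b = 0.3 |
|---|---|---|---|---|
| 11 | 0.90 | 5.7% | 7.9% | 11.6% |
| 11 | 0.85 | 5.8% | 8.2% | 12.4% |
| 14 | 0.90 | 5.9% | 8.8% | 13.6% |
| 14 | 0.85 | 6.0% | 9.2% | 14.7% |

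These are for one pairwise test at 5% without correction.

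**4. Under the planned analysis**

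Section 11.2 c plans a one-way ANOVA with Bonferroni corrections.

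- Three-group F-test at 5%, same b in both graft arms: 5.6–14.0%.
- Pairwise tests, if Bonferroni is taken over three comparisons (0.05/3 = 1.7% nominal): 2.0–2.1% at 0.1 mm, 3.0–3.7% at 0.2 mm, 4.9–6.6% at 0.3 mm. The largest value is about four times nominal (6.6/1.67).

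Correction lowers the absolute rate. It leaves the shift in the estimate as it was.

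**The case against.** The other side has good points, and most of them limit the claim.

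- **The outcome is not a caliper reading alone.** Item 8 also names scanned images and fixes the reference points by distance from the baseline margin. This narrows the reader's freedom. It does not close the gap, because reading of the scans is not masked either.
- **Codes already exist.** True, and a subject number by itself is therefore not the remedy. What is missing is a statement that the reader cannot tell the arm from the label.
- **The surgeon as reader.** A reader might infer that the surgeon will measure the casts. The documents do not say so. They are silent on who reads, which supports only that nothing prevents it. The case report form and study schedule, listed as possible attachments, were not available to check.
- **Other protections.** The reading step is not the only safeguard left. Allocation comes after extraction and after local eligibility is verified, and graft dimensions are standardised (Sections 3.3, 6.1, 6.3 a). These protect selection and delivery, and do not protect the measurement.
- **Limits of masking.** Visit cannot be fully hidden: the 12-month cast carries a crown, the pre-surgical CBCT has no implant, and the reference points come from the baseline cast. Trimming casts could damage the palatal surface on which the buccal-palatal width is measured.
- **Size.** The 0.1–0.3 mm is assumed. At 0.1 mm the false-positive rate in a single 5% test rises by one percentage point at most.

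**Conclusion.** The point holds. As written, the plan allows an unmasked person, possibly the operating surgeon, to read a judgement-based primary outcome with a directional hypothesis, although these materials could be read under a code. Adding that safeguard is a cheap improvement that should be made, and it does not alter the sample size.

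Its size is conditional. If readings favoured the grafts by 0.1–0.3 mm, the estimate would move by that amount. False positives would be about 6–15% in one uncorrected 5% test, or about 2–7% against 1.7% with Bonferroni over three pairwise tests. This assumes no true effect, a constant shift, 11–14 per group and SD 0.85–0.9 mm.

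Three stronger readings are not supported. The 6–15% is not this trial's error rate, since no document gives a reading bias. The trial has not been shown to be biased, since masked reading may be intended but not written down. Nor would coding remove all assessor bias: it removes the label as a source of knowledge when casts and images are read. Impression-taking and chairside measures such as gingival level, tissue thickness and probing depth would stay unmasked.

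**What to change.** Add to Sections 8.3 and 6.3 b:

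1. Casts, scans, CBCT images and radiographs carry a code that does not reveal arm.
2. The 3 mm and 6 mm reference points are transferred from the baseline cast before or during masked reading.
3. Readings are made by an existing sub-investigator who neither operated on nor allocated that patient.
4. Readings are locked before arm is revealed.

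Do not require masking of visit or trimming of casts. If the palatal donor site is covered, the cover must leave the palatal measuring surface intact.

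The cost is labelling time and a few sentences of protocol text, with no added visits, procedures or subjects. No new staff are needed provided that, for each patient, at least one existing sub-investigator meets condition 3. The documents do not state this, so it should be confirmed. If one of the two checkers in Section 10.1 becomes the reader, the plan should say how the second check is kept. Masking will be incomplete, because graft contour may hint at the arm.
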